### 4.4 Multicenter studies

Analysis will not be assessed for individual investigator sites due to the low expected number for enrollment within each investigator site.

### 4.5 Multiple comparisons/multiplicity

No statistical testing is planned; therefore, this section is not applicable for this study.

### 4.6 Use of an efficacy subset of subjects

No efficacy data are collected; therefore, this section is not applicable for this study.

### 4.7 Examination of subgroups

There is no subgroup analysis planned. However, the majority of summaries will be presented for all subjects, and separately by age cohort, by infusion duration and by subject group. In addition, selected summaries of Important protocol deviations (IPDs), AEs, vital signs and ECG findings and parameters will be provided by country of enrollment (Hungary and rest of the World).

### 4.8 Time points by infusion duration

The time points relative to infusion initiation for respective assessments will be as follows: In case value of blood pressure at the “≤1 hr pre-infusion with low PCS BP” time point is low PCS, the additional timepoint will be listed only and not included in summary tables.

- Vital signs time points for 15 min infusion:
  - ≤ 1 hr before initiation of iv BRV
  - 5 min after initiation of iv BRV
  - 10 min after initiation of iv BRV
  - 15 min after initiation of iv BRV
  - 30 min after initiation of iv BRV
  - 60 min after initiation of iv BRV.
  - 2 hr after initiation of iv BRV, only SBP and DBP will be collected.
- Vital Signs time points for Bolus:
  - ≤ 1 hr before initiation of iv BRV
  - ≤ 2 min after initiation of iv BRV

- 
- 5 min after initiation of iv BRV
  - 15 min after initiation of iv BRV
  - 30 min after initiation of iv BRV
  - 60 min after initiation of iv BRV
  - 2 hr after initiation of iv BRV, only SBP and DBP will be collected.
- Electrocardiogram time points for 15 min infusion:
    - $\leq 1$  hr before initiation of iv BRV
    - 5 min after initiation of iv BRV
    - 10 min after initiation of iv BRV
    - 15 min after initiation of iv BRV
    - 30 min after initiation of iv BRV
    - 60 min after initiation of iv BRV
    - 2 hr after initiation of iv BRV
  - Electrocardiogram time points for Bolus:
    - $\leq 1$  hr before initiation of iv BRV
    - $\leq 2$  min after initiation of iv BRV
    - 5 min after initiation of iv BRV
    - 15 min after initiation of iv BRV
    - 30 min after initiation of iv BRV
    - 60 min after initiation of iv BRV
    - 2 hr after initiation of iv BRV
  - Pharmacokinetic time points for 15 min infusion and Bolus:
    - $\leq 1$  hr before initiation of iv BRV
    - 15 min after initiation of iv BRV
    - 3 hr after initiation of iv BRV.

#### **4.9 Handling of data from open-label study**

Medical and procedural history, AEs, and prior and concomitant medication data for subjects coming from open-label study will only be documented within the open-label study and will be transferred into EP0065.

## 5 STUDY POPULATION CHARACTERISTICS

### 5.1 Subject disposition

Subjects who were screen failures, broken down by primary reason for screening failure, will be presented overall for all subjects screened.

A summary of disposition of subjects will be provided for all screened subjects. The date of first subject in (date of first Screening Visit), date of last subject out (date of last contact), number of subjects screened, number of subjects in each analysis set (SS-iv, SS and PK-PPS), number of subjects in the SS-iv receiving 15 minutes infusion and number of subjects in the SS-iv receiving bolus infusion will be summarized overall, by country and by investigator site. Subjects who transferred sites will be summarized according to their original site.

A summary of disposition of analysis sets will be provided for the SS including the number and percentage of subjects receiving 15 minutes infusion / bolus in each analysis set:

- The number and percentage of subjects in the SS
- The number and percentage of subjects in the SS-iv
- The number and percentage of subjects in the PK-PPS

A summary of disposition and discontinuation reasons will be presented overall for the SS-iv and the SS. The following information is included:

- The number and percentage of subjects starting the study, defined as having signed an informed consent.
- The number and percentage of subjects completing the study, defined as having received at least 1 iv BRV dose and completed at least one assessment at TC-1. This definition differs to the completed subjects from the eCRF.
- The overall number and percentage of subjects discontinuing the study early, and the number and percentage of subjects discontinuing by primary reason for discontinuation
- The number and percentage of subjects starting the Screening Period
- The number and percentage of subjects completing the Screening Period
  - Complete is defined as a non-missing informed consent date.
- The reasons for discontinuing during the Screening Period
- The number and percentage of subjects starting the IOB treatment Period
  - Start is defined by attending Visit 2.
- The number and percentage of subjects completing the IOB treatment Period
  - Complete is defined as receiving oral BRV for at least 2 days during the IOB treatment period.
- The reasons for discontinuing during the IOB treatment period
- The number and percentage of subjects starting the iv PK Period

- Start is defined by attending Visit 3.
- The number and percentage of subjects completing the iv PK Period
  - Completed is receiving at least one iv BRV dose during the iv PK Period.
- The reasons for discontinuing during the iv PK Period.
- The number and percentage of subjects starting down-titration (Follow-up Period)
  - Start is defined by having at least one down-titration BRV treatment.
- The number and percentage of subjects starting the Safety Period
  - A subject is considered as starting the Safety Period if their date of study termination is at least 12 hours after the last BRV treatment received during down-titration.

A summary of discontinuations due to AEs for the SS-iv will present the number and percentage of subjects who discontinued this study due to AEs overall, and by type of AE. The table will be repeated for the SS.

The following listings will be provided for all subjects screened: subjects who did not meet study eligibility criteria, subject disposition, subject analysis sets, subjects excluded from at least one analysis set, study discontinuation, and visit dates.

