### 3.2.5 Analysis periods

This study consists of a Screening Period, an IOB Treatment Period, an iv PK Period, a Follow-up Period and a Safety (BRV-free) Period, see [Section 2.3](#) for more details on these periods.

Start of Screening Period is defined as the date of enrollment and end of Screening Period is defined as immediately before first allocated BRV treatment.

Start of IOB Treatment Period is defined as the date of first allocated oral BRV treatment and end of IOB Treatment Period is defined as immediately before first iv BRV treatment.

Start of iv PK Period is defined as the date and time of first allocated iv BRV treatment and end of iv PK Period is defined as 12 hours after start of last iv BRV treatment.

Start of Follow-up Period is defined as 12 hours after start of last iv BRV treatment and end of Follow-up Period is defined for the following scenarios:

- Subjects who transition study: as TC-1
- Subjects who do not transition and do not down-titrate: as end of study
- Subjects who down-titrate: as 12 hours after start of last down-titration treatment.

Only subjects who down-titrate have a Safety (BRV-free) Period. Start of Safety Period is defined as immediately after the end of Follow-up Period (>12 hours after start of last down-titration treatment) and end is defined as end of study.

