The following summaries will also be produced by country of enrollment (Hungary and rest of the World) for all subjects, by infusion duration and by subject group for the SS-iv:

- Incidence of AEs – Overview
- Incidence of TEAEs

The following summary will also be produced by country of enrollment (Hungary and rest of the World) for all subjects and by infusion duration for the SS-iv:

- Incidence of TEAEs by Maximum Intensity

The following summaries will be produced overall and by age cohort and study period, for all subjects and separately by infusion duration and subject group for the SS:

- Incidence of TEAEs by Study Period
- Incidence of TEAEs Leading to Study Discontinuation by Study Period
- Incidence of Serious TEAEs by Study Period

The following summaries will be produced overall and by age cohort and study period, for all subjects and by infusion duration for the SS:

- Incidence of TEAEs by Maximum Intensity by Study Period

- Incidence of TEAEs by Maximum Relationship by Study Period

The following TEAE summaries will be produced overall and by age cohort for the SS:

- Incidence of Serious TEAEs - Subject Numbers
- Incidence of TEAEs Leading to Study Discontinuation - Subject Numbers

Additionally, incidence of TEAEs will be summarized by categorized relative time infusion for all subjects, and by age cohort for the SS-iv. The time of each AE relative to the start of the previous iv infusion will be calculated as described in [Section 3.2.4](#) and categorized into 0- $\leq$ 5 minutes,  $>5 - \leq 15$  minutes,  $>15$  to  $\leq 60$  minutes,  $>60 - \leq 12$  hours and  $>12$  hours.

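### SAP 5.1 counts only down-titraters under a row labelled Follow-up, although SAP 3.2.5 gives every infused subject a Follow-up Period; its Screening completion rule also cannot fail (minor)

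*SAP*

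**What the plan says.** **Follow-up in SAP 3.2.5 (Analysis periods).** "Start of Follow-up Period is defined as 12 hours after start of last iv BRV treatment". The section then gives three end points. For those who move to the long-term study it reads "Subjects who transition study: as TC-1". For those who neither transition nor down-titrate, the end is the end of study. For down-titraters, it is 12 hours after the start of the last down-titration treatment.

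**Follow-up in SAP 2.3 (Study design and conduct).** Down-titration is treated as part of the Follow-up Period, not as the whole of it.

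**Follow-up in SAP 5.1 (Subject disposition).** The row reads "The number and percentage of subjects starting down-titration (Follow-up Period", with the rule "Start is defined by having at least one down-titration BRV treatment". No other row counts entry into Follow-up.

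**Screening.** SAP 3.2.5 says "end of Screening Period is defined as immediately before first allocated BRV treatment". SAP 5.1 says of Screening: "Complete is defined as a non-missing informed consent date". Section 5.1 uses signed consent to define starting the study as well, and its next row asks for reasons for discontinuing during Screening.

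**Where the periods are used.** SAP 10.2.1 assigns each adverse event to the period in which it began and lists, for the Safety Set (SS), "Incidence of TEAEs by Study Period" and companion tables for discontinuation, seriousness, intensity and relationship. It names no by-period denominator. SAP 3.1 gives only a general rule that the denominator should suit the analysis.

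**The concern.** A reader of the report will look in the disposition table for the number of subjects behind each study period. For Follow-up that table will show only the down-titraters, while the adverse event tables will place events from all infused subjects in the same named period. This includes events picked up at the first telephone contact (TC-1), which the protocol (section 8.4) schedules for all infused subjects 1 to 3 days after the last infusion. Adverse events are a primary safety variable and the study is wholly descriptive, so counts and percentages are the result. Two populations under one period name make the by-period tables hard to interpret.

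The Screening rule is a separate fault. A completion criterion that consent alone satisfies cannot tell completers from those who stopped, yet the table also asks why subjects stopped.

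**Working it through.** The documents give no figure on this point to reproduce. The check is a comparison of definitions, followed by a small illustration.

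**1. Follow-up, by type of subject**

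| Subject | Follow-up under SAP 3.2.5 | Counted in the SAP 5.1 row |
|---|---|---|
| Infused, moves to long-term study | Yes, ends at TC-1 | No |
| Infused, neither transitions nor down-titrates | Yes, ends at end of study | No |
| Infused, down-titrates | Yes, ends 12 h after start of last down-titration treatment | Yes |
| Initiating oral BRV (IOB), stops before infusion, down-titrates | No start, because there is no last infusion | Yes |

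The two definitions agree only in the third line. The counts are guaranteed to match only if every infused subject down-titrates and nobody down-titrates without an infusion. The fourth line is possible under SAP 2.3: at least 4 doses in the IOB Treatment Period lead to down-titration, and 2 days of twice-daily dosing is 2 × 2 = 4 doses.

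Section 5.1 also disagrees with itself here. It defines study completion as one infusion plus an assessment at TC-1. For a subject who transitions, TC-1 is the end of Follow-up under 3.2.5. That subject completes the study and reaches the end of Follow-up without being counted as starting it.

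**2. Screening, within the sets the table uses**

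The table is restricted to SS-iv (at least one infusion) and SS (at least one BRV dose, oral or iv).

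- SS-iv: everyone was infused, so everyone completed Screening under any sensible rule.
- SS, IOB subjects and those initiating iv BRV (IIB): each has had a first allocated dose, so again there is no difference.
- SS, open-label (OLB) or prescribed-BRV (RxB) subject who stops before infusion: SAP 10.2 assumes BRV was taken on the first screening day, so on that reading the subject is in the SS. Protocol 7.2.2 foresees OLB subjects who discontinue BRV in Screening. Under 5.1 the subject completes Screening by having a consent date and also appears among those discontinuing in it.

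The fault therefore affects un-infused OLB and RxB subjects only.

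**3. The other periods**

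- IOB: 5.1 starts it at Visit 2, 3.2.5 at the first oral dose. An IOB subject who attends Visit 2 and takes no BRV is outside the SS, so the difference has no effect on the table.
- iv PK: 5.1 says "Start is defined by attending Visit 3", while 3.2.5 uses the first infusion. Only an SS subject on oral BRV who attends Visit 3 and is never infused differs. Section 5.1 shows that subject as started but not completed, since completion needs one iv dose.
- Safety (BRV-free) Period: at least 12 hours in 5.1 against more than 12 hours in 3.2.5, which is effectively the same.

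**4. Illustration of the Follow-up gap**

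Inputs: N = 50 infused (the planned approximate number, SAP 2.3); d down-titraters (not in the documents, assumed 5, 10 or 20); x = 3 subjects with a Follow-up event (assumed).

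- Share of the 3.2.5 population: x/N = 3/50 = 6%.
- Share of the 5.1 count: x/d = 3/5 = 60%, 3/10 = 30%, 3/20 = 15%.

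The second line is only what would follow if the 5.1 count were used as the denominator.

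**The case against.** The strongest reply is that 5.1 sets up no rival definition. The row counts subjects starting down-titration, and the bracket merely names the period in which down-titration falls, as SAP 2.3 would have it. That is a fair reading, and it makes the fault milder. It does not remove it: the table would still have no count of subjects entering Follow-up as 3.2.5 defines it, and the label would still suggest that it does.

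A reader might go further and infer that the SAP divides the Follow-up events of all infused subjects by the number of down-titraters, giving percentages that could pass 100%. The documents do not support that. Nothing links the disposition counts to the adverse event tables, SAP 3.1 asks for an appropriate denominator, and assigning events by period of onset points to the 3.2.5 boundaries. What stands is that the by-period denominator is not named.

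A reader might also infer that the Visit 2 and Visit 3 start rules corrupt the IOB and iv PK rows. Within the SS and SS-iv the first case is empty and the second nearly so. The blood pressure hold in protocol 5.2 delays an infusion until the low criterion is no longer met; it does not in itself stop a subject from entering the period. Moving the iv PK start to the first infusion would make it identical to the 5.1 completion rule, so completion would be 100% by construction.

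Finally, SS-iv is the primary safety set, its adverse event summaries combine all periods unless otherwise stated, and onset dates and times are listed. That limits the importance of the point.

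**Conclusion.** The point holds in a limited form and is minor. Section 5.1 conflicts with 3.2.5 and 2.3 on who is in Follow-up, or at best leaves the 3.2.5 Follow-up population uncounted under a label that suggests otherwise. Its Screening completion rule lets one subject be both a completer and a discontinuation.

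The size of the Follow-up gap is the number of infused subjects who do not down-titrate, offset by any un-infused down-titraters in the SS; the documents give neither number. The contrast of 6% with 15% to 60% rests on assumed counts and on a denominator the SAP does not state, so it is not an error built into the plan. The Screening fault rests on reading un-infused OLB and RxB subjects as members of the SS, which the treatment assumption in SAP 10.2 supports. Only descriptive disposition and by-period safety tables are affected; no test or sample size depends on them.

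**What to change.** In SAP 5.1:

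- Add a row for subjects who entered the Follow-up Period, using the 3.2.5 start.
- Keep started down-titration as its own row without the Follow-up label. Do not nest it under Follow-up, because an IOB subject may down-titrate without an infusion. State where such a subject is counted.
- Define Screening completion as receiving the first allocated BRV dose, which for OLB and RxB subjects is the first infusion.
- Leave the Visit 2 and Visit 3 start rules for the IOB and iv PK rows as they are. The existing row for completing the iv PK Period already gives the number infused, which is the 3.2.5 entry count.

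In SAP 10.2.1, add one sentence: by-period percentages use the number of subjects who entered that period under 3.2.5.

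The cost is SAP wording and reprogramming of one disposition table, with the denominator confirmed in the by-period programs. No new data are needed.

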## 5.2 Protocol deviations

IPDs defined in the IPD specification document, and additionally identified at the data evaluation meetings, will be listed. In addition, the number and percentage of subjects with at least one important protocol deviation will be summarized overall and by category of important protocol deviation for the SS-iv and the SS. The number and percentage of subjects with no important protocol deviations will also be summarized. These summaries will be presented overall and by age group for all subjects, and by infusion duration. A separate summary will be presented by country of enrollment (Hungary and rest of the World) for all subjects and by infusion duration.

All completed COVID-19 Impact eCRF pages, and other IPDs will be discussed in important protocol deviation meetings, including whether the deviation may have been caused by COVID-19.

All data collected from the COVID-19 Impact eCRF page will be listed.

## 6 DEMOGRAPHICS AND OTHER BASELINE CHARACTERISTICS

### 6.1 Demographics and other Baseline Characteristics

Demographic variables will be presented for the SS-iv and the SS. The variables to be presented are:

- Age at entry into EP0065 (in years for subjects aged >2 years at study entry, in months for subjects aged ≤ 2 years at study entry)
- Age at first diagnosis (in years and in months) (as defined in [Section 3.2.7](#))

- Duration of epilepsy (in years and in months) (as defined in [Section 3.2.8](#) )
- Categorized age at entry into EP0065:
  - EudraCT age categories:  $\geq 1$  month to  $< 24$  months,  $\geq 24$  months to  $< 12$  years,  $\geq 12$  to  $< 16$  years
  - Age categories for submission:  $\geq 1$  month to  $< 4$  years,  $\geq 4$  to  $< 16$  years
- Gender (male, female)
- Subject group (OLB, RxB, IOB, and IIB)
- Weight at Screening (kg)
- Weight at baseline (kg)
- Weight group at baseline ( $< 50$  kg,  $\geq 50$  kg)
- Height at Screening (cm)
- BMI at Screening ( $\text{kg}/\text{m}^2$ ) (as defined in [Section 3.3](#))
- Racial group (American Indian/Alaskan Native, Asian, Black, Native Hawaiian or Other Pacific Islander, White, Other/Mixed)
- Ethnicity (Hispanic or Latino or Not Hispanic or Latino)
- Country (Countries may include Czech Republic, France, Germany, Hungary, Italy, Ireland, Mexico, Poland, Spain, USA)
- VNS Status (VNS not used, VNS used; if used: VNS active, VNS not active)

The following listings will be provided by age cohort for all subjects screened:

- demographics at Screening
- childbearing potential at Screening
- historical seizure count (describing the type and number of seizures experienced in the 3 weeks prior to Screening)
- diagnosis of epilepsy (describing the primary disease, date of first epilepsy diagnosis and history of status epilepticus prior to the 1-month period before Screening)
- vagus nerve stimulation status at Screening
- family medical history (family medical history is only collected for subjects with potential drug-induced liver injury and will describe the medical conditions including start and stop dates)
- lifestyle (lifestyle information is only collected for subjects with potential drug-induced liver injury and will describe the alcohol- and illicit drug use within past 6 months)

## 6.2 Medical history and ongoing diseases

The number and percentage of subjects with a medical history condition, including both previous and ongoing conditions at the time of study entry (Screening), are summarized separately overall

and by MedDRA primary system organ class (SOC) and preferred term (PT) for the SS-iv. Additionally, the number and percentage of subjects with ongoing medical conditions are summarized overall (i.e. any ongoing medical conditions at Screening) and by primary SOC and PT. A subject data listing for the previous and ongoing medical history conditions will be provided for the SS together with the medical history glossary.

### **6.3 Prior and concomitant medications**

Prior medications include any medications that started prior to the date of first dose of iv BRV. Only prior medication which is ongoing or has an end date in the 2 weeks prior to screening will be included in summaries. Prior medication with an end date prior to the 2 weeks before screening will be listed only. Concomitant medications are medications taken on at least one day in common with the iv PK Treatment Period. Medications may be both prior and concomitant. Medications which started after the day of the last iv BRV treatment will be categorized as follow-up medications.

For OLB subjects only medication which started during the EP0065 study will be recorded in the EP0065 study. Information of medication which started before EP0065 study start will come from the respective OLB study. Only medications with a stop date  $\leq$  14 days prior to start date of EP0065 will be summarized in EP0065.

Antiepileptic drugs (AED) will be identified using an internal UCB AED list (file: AEDs\_ATCs\_SEP2017\_FINAL\_benzo\_groups\_23JUL2019.xls).

Subject data listings for prior, concomitant and follow-up AEDs, and prior, concomitant and follow-up non-AEDs will be provided separately together with a listing of medication glossary including all reported medications.

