N01263 is a completed open-label, multicenter, fixed 3-step up-titration, adjunctive therapy study of the PK, safety, and efficacy of BRV in 100 subjects ≥ 1 month to <16 years of age with epilepsy. Doses of BRV (oral solution) were adjusted by body weight and did not exceed a maximum of 50mg/day, 100mg/day, and 200mg/day for each titration step. A total of 100 subjects enrolled in N01263: 99 subjects received study drug and were included in the Safety Set. Results from N01263 indicate that BRV was generally well tolerated and that the safety profile in pediatric subjects was consistent with the known safety profile in adult

subjects. In general, there were no clinically meaningful changes in laboratory parameters, vital signs, or ECG parameters. Trough plasma BRV concentrations increased proportionally to the dose.

N01266 is an ongoing open-label, multicenter study to evaluate the long-term safety and efficacy of bid administration of BRV oral solution and oral tablets in pediatric subjects with epilepsy who are receiving ≥ 1 AED other than BRV; the maximum allowable BRV dose is 5mg/kg/day not to exceed 200mg/day in subjects with body weights >40 kg. N01266 was initially designed as a long-term follow-up to N01263, which enrolled only subjects with either focal epilepsy or generalized epilepsy but was amended to also allow direct enrollment of subjects 4 years to <17 years of age who have focal epilepsy. Over 200 subjects have enrolled in N01266.

In addition to oral formulations, iv formulations of AEDs are particularly helpful as short-term replacements when use of oral formulations is not possible or feasible (eg, pre and postoperative patients, patients with acute gastrointestinal disorders, patients with acute swallowing disorders). Brivaracetam injection has been approved for use as adjunctive therapy in the treatment of POS in patients 16 years of age and older with epilepsy and may be used when oral administration of BRV is temporarily not feasible. Treatment with BRV may be initiated with tablets, oral solution, or solution for injection.

The current study, EP0065, is planned to evaluate the PK, safety, and tolerability of iv BRV administered as a 15-minute infusion and bolus (up to 2-minute infusion) in subjects ≥ 1 month to <16 years of age with epilepsy.

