7.8.3 Rescue medication

Investigators may administer rescue medication in accordance with medical judgment at any time during the study. No rescue medication will be supplied by UCB.

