### 2.3 Study design and conduct

EP0065 is a Phase 2 multicenter, open-label study to evaluate the PK, safety, and tolerability of iv BRV administered as a 15-minute iv infusion and an iv bolus (up to 2-minute infusion) in subjects  $\geq 1$  month to  $< 16$  years of age with epilepsy.

Study medication is defined by iv infusion of BRV administered as a 15-minute iv infusion or an iv bolus (up to 2-minute infusion). Oral BRV can be administered during EP0065 but will not be considered as study medication for EP0065.

Approximately 50 enrolled subjects will receive iv BRV in the following age-based cohorts (approximately 12 subjects/cohort):

- Cohort 1:  $\geq 12$  to  $< 16$  years
- Cohort 2:  $\geq 6$  years to  $< 12$  years
- Cohort 3:  $\geq 2$  to  $< 6$  years
- Cohort 4:  $\geq 1$  month to  $< 2$  years

The age at Screening Visit will be the determining factor for age cohort assignment. Each age cohort will have approximately 50% of subjects with iv BRV infusion and 50% with bolus BRV.

The following subjects will be eligible for enrollment in EP0065:

- Open-label BRV (OLB) subjects: currently receiving oral BRV as participants in a long-term, open-label study
- Prescribed BRV (RxB) subjects: currently receiving prescribed oral BRV from commercial supply
- Initiating Oral BRV (IOB) subjects: not currently receiving BRV; first dose of BRV in EP0065 will be oral tablet or solution
- Initiating iv BRV (IIB) subjects: not currently receiving BRV; first dose of BRV in EP0065 will be by iv Infusion

For OLB and RxB subjects, the maximum BRV dose is 5mg/kg/day (rounded). For IOB and IIB subjects, the maximum BRV dose is 4mg/kg/day. Throughout the study, no subject may receive a dose greater than BRV 200mg/day. Subjects will receive oral BRV (tablets or oral solution) in equally divided doses; BRV oral solution may be given by enteric administration (eg, by feeding tube) based on subject need.

The EP0065 study periods and visits are described below. The PK assessments will be made during the iv PK Period only and safety data will be collected throughout the study, with intensive collection of safety data with each iv BRV dose administered. A Schedule of Study Assessments is provided in the protocol for the Screening through iv PK Periods and for the Down-Titration Period and Safety (BRV-free) Periods (for subjects not continuing BRV).

- Screening Period (1 to 10 days)

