## 2.4 Determination of sample size

The primary objective of the study is to evaluate the PK, safety, and tolerability of BRV given intravenously. The plan for approximately 50 enrolled subjects (4 age cohorts of approximately 12 subjects each) to receive iv BRV was deemed clinically appropriate for the evaluation of the PK, safety, and tolerability of iv BRV administration in subjects  $\geq 1$  month to  $< 16$  years of age with epilepsy. No formal sample size calculation has been performed.

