##### Imputation of Partial Start Dates

- If only the month and year are specified and the month and year of first dose of iv BRV is not the same as the month and year of the start date, then use the 1st of the month.
- If only the month and year are specified and the month and year of first dose of iv BRV is the same as the month and year of the start, then use the date of first dose of iv BRV.
- If only the year is specified, and the year of first dose of iv BRV is not the same as the year of the start date, then use 1 Jan of the year of the start date.
- If only the year is specified, and the year of first dose of iv BRV is the same as the year of the start date, then use the date of first dose of iv BRV.
- If the start date is completely unknown and the stop date is unknown or not prior to the date of first dose of iv BRV, then use the date of first dose of iv BRV.

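### Read literally, SAP 6.3 leaves OLB subjects' ongoing AEDs, and drugs started and stopped between Screening and the first infusion, out of the medication summary tables

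*SAP*

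**What the plan says.** SAP 6.3 gives a definition and a filter for prior medication. The definition is "Prior medications include any medications that started prior to the date of first dose of iv BRV". The filter is "Only prior medication which is ongoing or has an end date in the 2 weeks prior to screening will be included in summaries". Drugs that ended earlier than that are listed only. No reference date is given for ongoing. A drug is concomitant if it shares at least one day with the iv PK Period.

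For OLB subjects a further sentence applies: "Information of medication which started before EP0065 study start will come from the respective OLB study. Only medications with a stop date" no more than 14 days before EP0065 start go into the summaries. Ongoing drugs are not mentioned there.

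SAP 6.3.2 promises counts of AEDs taken before and together with iv BRV for the whole SS-iv. SAP 4.9 says that OLB medication data are transferred into EP0065. SAP 4.2.3 leaves a completely unknown stop date unimputed. It also moves a partial start in the same month or year as the first iv dose to the date of that dose. Only the bullet for a wholly unknown start looks at the stop date: "If the start date is completely unknown and the stop date is unknown or not prior to the date of first dose of iv BRV".

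Protocol 7.8.3 states: "Investigators may administer rescue medication in accordance with medical judgment at any time during the study".

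**The concern.** For OLB subjects the literal rule works backwards. A drug stopped last week is tabulated, while one taken during the infusion is not. The general rule has a different gap. It looks back from Screening and never covers an end date that falls between Screening and the day of first infusion.

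The study has no control group and no hypothesis tests, so the descriptive tables are its main output. Other drugs are an obvious alternative explanation for sedation, respiratory or blood-pressure findings. Under SAP 10.2 every AE is treatment-emergent from Screening for OLB and RxB, and from the IOB Treatment Period for IOB. SAP 10.2.1 combines all study periods unless otherwise indicated. TEAEs would therefore be counted in a window where short-course drugs appear in no medication table.

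**Working it through.** There is no figure in the plan to reproduce: "No formal sample size calculation has been performed". The check applies the SAP 6.3 rules to example drugs.

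**Set-up.** First iv dose F = day 0 and Screening S = day −5. EP0065 start is taken as the Screening day.

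- Prior: start < F.
- In the prior table: prior, and either ongoing or S − 14 ≤ end ≤ S. Here S − 14 = −19.
- Concomitant: started by the last iv day, with no end date or end ≥ F.
- OLB filter, applied only to drugs started before EP0065: S − 14 ≤ end ≤ S.

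Because ongoing has no reference date, three readings were tried: no end date, ongoing at Screening, and ongoing at first iv dose.

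| Drug (start, end) | Non-OLB prior table | Non-OLB concomitant table | OLB prior table | OLB concomitant table |
|---|---|---|---|---|
| AED (−400, none) | yes | yes | **no** | **no** |
| AED (−400, −15) | yes | no | yes | no |
| AED (−400, −35) | no | no | no | no |
| Drug (−40, −2) | only if ongoing at Screening | no | no | no |
| Single dose (−2, −2) | **no** | **no** | **no** | **no** |
| Dose on day of first iv (0, 0) | no | yes | no | yes |
| Drug (−3, none) | yes, unless ongoing means at Screening | yes | same as non-OLB | yes |

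The bold cells are the same under all three readings.

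**Windows** (Protocol 8.1 and 8.2). For OLB, RxB and IIB, Day −10 to Day −1 is up to 10 days. For IOB, Day −20 to Day −1 is up to 20 days. The IOB Treatment Period, where IOB AEs are treatment-emergent, takes up to 10 of those 20 (Day −10 to Day −1). For IIB, AEs become treatment-emergent only from the iv PK Period, so the window does not overlap.

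**Size of the OLB effect.** The plan says "Approximately 50 enrolled subjects will receive iv BRV in the following age-based cohorts" but does not say how many are OLB. Assume that all 50 take an ongoing AED, that k of them are OLB, and that OLB subjects start no new AED in EP0065. A literal concomitant-AED table would then show 100 × (50 − k)/50 percent instead of 100%:

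- k = 5: 45/50 = 90%
- k = 12: 38/50 = 76%
- k = 25: 25/50 = 50%
- k = 38: 12/50 = 24%

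The values of k are illustrations, and the loss of k/50 is a ceiling for each.

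**Edge case in SAP 4.2.3.** Take a start recorded as June 2019, a stop on 3 June 2019 and a first iv dose on 20 June 2019. The start is imputed as 20 June, which is 20 − 3 = 17 days after the recorded stop. The drug is not prior, because its start is not before 20 June. It is not concomitant, because it ended on 3 June.

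**The case against.** The strongest reply is that the OLB sentence is only a look-back limit for stopped drugs imported from the open-label study. The general rule keeps ongoing drugs with no OLB exception, SAP 6.3.2 covers the whole SS-iv, and the data are transferred. The SAP change log (13.3) describes the rule as one about drugs that finished 2 weeks or more before Screening. This is probably the intent, and it stands as an argument about intent. It does not remove the word that restricts the OLB sentence, and nothing says which rule prevails.

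Several stronger readings are tempting but not supported:

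- *Nearly every OLB child would lose an AED.* A reader might infer this because the long-term study in the Protocol Introduction concerns "pediatric subjects with epilepsy who are receiving ≥ 1 AED other than BRV". That describes one feeder study. EP0065 inclusion criterion 7 counts BRV itself as the required AED, so a child on BRV alone is eligible.
- *Rescue use goes unreported.* Rescue on Day 1 or in the iv PK Period is concomitant and is summarized. That is where the intensive ECG and vital-sign data lie, and Protocol 12.4.1.1 summarizes the primary safety variables for that period. Exclusion criterion 6 also bars children judged likely to need rescue in the IOB Treatment or iv PK Periods.
- *Imputation hides long-standing AEDs.* An AED with an unknown or year-only start that is still being taken may be set to Day 1, but it stays in the concomitant table. SAP 4.2.3 also treats undeterminable cases as concomitant. Only the combination of a partial start in the same month or year as the first dose and a known earlier stop fails.

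The listings in SAP 6.3 keep all these drugs with subject-level dates, and those dates are what attribution of a single event would rest on.

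**Conclusion.** Two gaps hold on the text as written, and both concern the summary tables only. Ongoing pre-study AEDs of OLB subjects are left out, against the general rule and SAP 6.3.2. A drug started and stopped between Screening and the day of first iv BRV is in no summary, in any subject group. The first gap produces wrong tables only if the OLB sentence is programmed literally. The second holds under each of the three readings of ongoing. The 4.2.3 problem is an edge case.

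The documents do not support saying that background treatment will be misreported. That outcome depends on literal programming, short-course rescue is not background treatment, and the OLB count is unknown. Severity is minor: all analyses are descriptive, the listings are intact and no primary variable changes.

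**What to change.** **SAP 6.3, OLB sentence:** *medications ongoing at EP0065 start, or with a stop date no more than 14 days before EP0065 start, will be summarized.*

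**SAP 6.3, general rule:** *prior medication that is ongoing at Screening, or has an end date on or after 14 days before Screening, will be summarized.* Add that a prior drug with no recorded end date counts as ongoing, so that one begun during Screening and continued is also covered.

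In the example, the OLB background AED then enters both tables. The single dose at day −2 enters the prior table, since −2 is later than −19. The AED that ended at day −35 stays listed only.

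**SAP 4.2.3:** add to the partial-start bullets the stop-date condition already in the unknown-start bullet, so that an imputed start never falls after a recorded stop.

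Keep the 6.3 definition of concomitant. Do not call a drug concomitant merely because it was ongoing at Screening. Screening can be up to 20 days before Day 1, and a drug stopped in between would then be misclassified.

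The cost is a few sentences and derivation code. No new data are needed, because the OLB records are already transferred under SAP 4.9.
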